Official Study Title: Use of liposomal bupivacaine for postoperative pain management after arthroscopic rotator cuff repair

ClinicalTrials.GOV ID Number: NCT03149887

Protocol Date: 2/13/2019

Scientific Background:

Arthroscopic rotator cuff repair is among the most painful of orthopedic surgeries. Hundreds of thousands of these procedures are carried out in the U.S. each year. Many involve the use of a brachial plexus nerve block, which serves to control pain for 12 to 14 hours. However, when the block wears off, many patients are left with severe pain. This severe pain is must then be managed at home with oral opioids, which have numerous undesirable side effects, and may lead to chronic opioid dependence. Thus, any therapy which might reduce the pain burden on these patients and therefore reduce opioid use and side effects, would be advantageous.

Recently, a long-acting form of bupivacaine, prepared in liposomes, has been approved for use by injection in the surgical field, though not for peripheral nerve blockade. The drug has been used to improve postoperative pain after total knee arthroplasty and total hip arthroplasty when injected in the peri-articular tissues by the orthopedist, as well as in other surgeries, both orthopedic and non-orthopedic. Liposomal bupivacaine is FDA approved for administration into the surgical site to produce postsurgical analgesia and mitigate pain, but it hasn't been yet used for rotator cuff surgery.

Study Objectives:

The purpose of this research study is to determine if liposomal bupivacaine, injected into the surgical field during rotator cuff repair surgery provides superior analgesia post operatively (after the standard nerve block resolves) compared with standard therapy.

The primary outcome measure is pain score at 24 hours, which will be obtained by phone follow up. Secondary outcomes include maximal pain score on postoperative day 1, 2 and 3, total oral opioid morphine equivalent after 3 days, and occurrence of typical opioid side effects (nausea, vomiting, and/or drowsiness). In addition to follow up phone call on POD 1, patients will keep a pain diary, documenting pain scores and opioid use for the first 72 hours, which will be collected by the surgeon in his office at the first postoperative visit. Any adverse occurrences related to nerve blockade or prolonged bupivacaine effect will also be recorded. In addition, the development of chronic pain at the surgical site will be assessed and compared between the two groups, with appropriate referral to the chronic pain service for any patient who experiences this outcome.

Study Design and Methods:

This randomized, double blind, placebo-controlled study was approved by the University of Pittsburgh Institutional Review Board (PRO17020089), and registered with ClinicalTrials.gov (NCT03149887).

Patients will provide written consent for participation on the day of surgery. A computer-generated randomization number will be assigned by the Investigational Drug pharmacy at our institution, and patients will be accordingly designated to receive either liposomal bupivacaine or normal saline injection. The pharmacy will then prepare the study drug (either liposomal bupivacaine or saline), packaged in a fashion that cannot be recognized by the investigators, and then sent to the operating room for injection by the surgeon.

The patients and the research team will be blinded to which group the patients are in. It is not possible to prepare an effective placebo solution for the liposomal bupivacaine, so the surgeon will remain un-blinded. Other members of the research team will determine the primary and secondary outcomes, and the

surgeon will not take part in the data collection for primary or secondary analyses. By the time of the first surgical follow up examination, the outcomes will have been determined and recorded by investigators.

All patients will undergo standard interscalene nerve blocks with plain bupivacaine 0.5% or ropivacaine 0.5%, with volumes varying between 15 and 20 ml based upon visual analysis of injectate spread by the anesthesiology team. Once an effective nerve block is demonstrated (inability to raise the arm, biceps weakness, loss of sensation over the C4 and C5 dermatome regions), patients are to be taken to the operating room. Anesthesia for the procedure will consist of the interscalene nerve block, along with infusion of propofol for sedation, accompanied by small doses of ketamine (20 to 40 mg), and dexmedetomidine (12-20 mcg).

Per our institutional review board, it is essential that the joint capsule be closed before injection of liposomal bupivacaine, since liposomal bupivacaine is not approved for intra-articular use. If the capsule cannot be closed for surgical reasons at the end of the procedure, an enrolled patient will be removed from the study at that point, and will not receive the injection of the study drug. The rotator cuff repairs are to be performed in the beach chair position by a single surgeon with either three or four routine portals, including anterior, posterior, and one or two lateral portals. The total dose of liposomal bupivacaine will be 266 mg, diluted with an additional 40 ml of saline to a total of 60 ml. In control patients, 60 ml of normal saline are to be injected in like fashion. In each group, the sixty milliliters of solution was divided into two thirty milliliter syringes. After completion of the arthroscopic rotator cuff repair, which includes a subacromial decompression, an eighteen gauge spinal needle will be placed under direct vision into the subacromial space and secured with tape. The arthroscopic instrumentation will be removed and each of the three or four portals then infiltrated at the superficial skin and the deep tissue, including the deltoid muscle surrounding the portal tract, with equally divided amounts from one of the thirty milliliter syringes using a one and one-half inch twenty-two gauge needle. The portals will then be closed with absorbable suture and the remaining thirty milliliters of solution in the second syringe injected into the subacromial space via the previously placed eighteen gauge spinal needle. Finally, the needle is to be removed, and the dressings as well as a sling are applied.

At the conclusion of surgery, patients will be taken to PACU, where they report their NRS pain score, and intravenous dilaudid will be provided for analgesia for scores greater than 3/10. Patients are to be called the day after surgery (approximately 24 hrs after leaving the hospital), and asked about their pain experience. Specifically, for the primary outcome, they will be asked to relate NRS pain score, at the time that the interscalene block had, in their perception, completely resolved (restoration of hand sensation, movement at elbow, and onset of pain at the shoulder). For the secondary analyses of pain and opioid use, patients will record their NRS scores in a 72 hour postoperative diary, for pain at rest and (for patients instructed to do so) when participating in range-of-motion exercises ("pendulum swings"). In addition, the participants are to record oral opioid doses, use of other analgesics (such as acetaminophen), and any side effects that they encounter. Patients also will rate their satisfaction regarding pain management at the end of the 72 hour period. The pain diary will then be brought to the one-week follow up appointment, collected by the research team, and the data transcribed. Finally, the surgeon will note any patient who develops chronic pain requiring referral to a pain management specialist.

Eligibility Criteria:

Those eligible for inclusion are adults ages 18-65, in American Society of Anesthesiologist physical status class 1 through 3, who are undergoing arthroscopic rotator cuff repair, either primary or revision. Exclusion criteria include pre-existing nerve damage, pre-existing chronic pain in the shoulder joint, opioid use for greater than 30 days preoperatively, coagulopathy, renal or liver disease, pregnancy, allergy

to local anesthetics, patient refusal, infection at the site of injection, age over 65 years, or incompetent rotator cuff/joint capsule.

Statistical Considerations:

Sample size is calculated based on the a priori assumption that liposomal bupivacaine would result in a reduction of pain scores at the time of block resolution by two or more units in the NRS rating (0 to 10 scale). The minimum clinically important difference for acute pain, acute postoperative pain, and shoulder-related pain range between 1 and 2 (out of 10), We chose a change in the score of 2 units to represent a clinically important improvement in pain control. To detect a decrement of 2 units or more with a two-tailed significance level of 0.05 and a power of 0.8, a sample size of 50 is required, 25 in each group.

The analysis of data will be carried out using SAS software, Version 9.4, of the SAS System for Windows (Copyright 2016 SAS Institute Inc., Cary, NC, USA). Continuous measures, such as pain scores, oral morphine equivalents, and some demographic information, are presented as mean \pm standard deviation, and compared using t-tests. Frequency distributions of categorical variables, such as opioid related side effects, and other demographic information, are compared using the Fisher's exact test. Opioid use will be converted to oral morphine equivalents. A two-tailed p value of <0.05 is considered to reflect statistical significance, while a difference in the primary outcome of 2 or more on the NRS scale is our threshold for clinically meaningful change

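### Does the daily maximal pain score mix rest and exercise scores, so that it is not the same measure in every patient?

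*Combined protocol and SAP*

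**What the plan says.** All references are to the combined protocol and SAP.

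- **Study Objectives** names the secondary outcome: "maximal pain score on postoperative day 1, 2 and 3". It does not say under what condition the pain is rated.
- **Study Design and Methods** (postoperative follow-up) gives the source: "For the secondary analyses of pain and opioid use, patients will record their NRS scores in a 72 hour postoperative diary". The scores are "for pain at rest and (for patients instructed to do so) when participating in range-of-motion exercises".
- **Study Design and Methods** (blinding) says that no effective placebo solution can be prepared, "so the surgeon will remain un-blinded". It also keeps the surgeon out of data collection for the primary and secondary analyses. The document does not say who gives the exercise instruction.
- **Statistical Considerations** covers "Continuous measures, such as pain scores, oral morphine equivalents, and some demographic information" with means, standard deviations and t-tests. It does not separate rest from movement. The sample size is set for the primary outcome only: 2 NRS units, two-sided 0.05, and "a power of 0.8, a sample size of 50 is required, 25 in each group".

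**The concern.** Taken at its plainest, a maximal score is the highest one recorded. On that reading an exercise score can set the maximum for some patients and cannot for others. Exercise also happens after the study injection, so randomisation does not balance it. Whether a patient takes part may depend on how much pain there is, which is what the drug is meant to change.

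Two things would be at stake. With equal exercising in both arms, mixing the two kinds of score widens the spread and costs power. If patients with less pain exercise more, the better-treated arm collects more exercise scores, and the comparison hides part of a real benefit. Because the surgeon knows the allocation, blinding alone cannot guarantee equal exercising in the two arms.

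**Working it through.** **Step 1: what the text fixes.** Rest scores are asked of all patients. Exercise scores need both an instruction and participation. The document presents these as two conditions in one diary and nowhere says they are combined. Under a rest-only maximum the issue disappears. It also disappears on any day when nobody or everybody exercises. The diary form is not in the document, so a single daily worst-pain item answered by everyone is possible too.

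**Step 2: an SD for illustration.** No SD is stated, so the figure of 25 per arm cannot be reproduced forwards. Solving backwards with the t-test (25 per arm, two-sided 0.05, power 0.80) gives an effect size of 0.809, so SD = 2/0.809 = 2.47. This SD and the 2-unit effect belong to the primary outcome and are borrowed here. The plan makes no power claim for the daily maximum.

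**Step 3: half of each arm exercises (assumed).** Let d be the points that exercise adds to the day's maximum (assumed 1, 2 or 3). The difference stays 2.0, and SD = sqrt(2.47² + 0.25d²).

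| d | SD | Power for 2 units |
|---|---|---|
| 1 | 2.52 | 0.784 |
| 2 | 2.67 | 0.738 |
| 3 | 2.89 | 0.668 |

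**Step 4: exercising falls with the patient's own pain (assumed).** The pooled difference is 2.0 − d × (share exercising on drug − share on control). The simulation used 20,000 trials per setting, rest means of 6 and 4, and a logistic chance of exercising centred at 5.

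| Slope per NRS point | Shares, control vs drug | Difference, d = 1, 2, 3 | Power, d = 1, 2, 3 |
|---|---|---|---|
| 0.2 | 45% vs 55% | 1.91, 1.81, 1.72 | 0.783, 0.727, 0.642 |
| 0.4 | 42% vs 58% | 1.84, 1.67, 1.52 | 0.788, 0.726, 0.626 |
| 0.6 | 39% vs 60% | 1.78, 1.57, 1.36 | 0.782, 0.726, 0.605 |

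Rest-only power in these runs is 0.80. A repeat run agreed within about 0.02 on both difference and power. For d = 1 and 2, power is within about 0.01 of Step 3, so dependence on pain adds almost no loss of power there. It does shrink the estimate.

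**Step 5: how far this is an upper bound.** Step 4 adds all of d to every exerciser's daily rest maximum, as if the session coincided with the worst rest pain of the day. Suppose instead that rest pain at the session is 1 point below the day's worst (assumed). With slope 0.6 and d = 1, 2, 3, the differences are then about 2.0, 1.8 and 1.6, and power about 0.80, 0.78 and 0.72.

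**Step 6: false positives.** If the drug does nothing to pain, exercising that depends only on the patient's own pain is the same in both arms. The simulated type I error was 0.046 to 0.052. It rises only if the shares differ for some other reason. With 60% vs 40% exercising, no drug effect and SD 2.5, the false shift is d × 0.2 = 0.2, 0.4 or 0.6 points, and type I error is 0.06, 0.08 or 0.11. Nothing in the document points to such an imbalance.

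**The case for a change.** The strongest case for a change is that the wording permits two different outcomes and chooses neither. One of them depends on behaviour after treatment, and an analyst could pick between them after seeing the results. Defining the tested outcome as the maximal rest score, the only score asked of everyone, would cost a line of text and no patients.

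The ambiguity stands, and so does the arithmetic on its assumptions. The step from there to a required change does not:

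- Pooling is inferred from silence.
- A rest-only definition is not plainly better. It takes movement pain out of the tested outcome, and after shoulder surgery worst pain whatever the activity is a legitimate thing to measure. Reasonable statisticians would differ.
- The surgeon's knowledge of allocation shows only that imbalance is possible. No passage says that the surgeon gives the exercise instruction or varies it by arm, and the patients are blinded.

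**Conclusion.** No change to the plan is called for. This is a gap in the definition of one secondary outcome, and analysts with rest and exercise scores recorded as separate conditions can fill it sensibly: settle before unblinding which scores form the maximum, and show the two conditions separately. Which maximum to test is a trade-off for the investigators.

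If the scores were pooled, a true 2.0-point difference would show as 2.0 with equal exercising and as 1.91 down to 1.36 with pain-dependent exercising. Power would be about 0.78 to 0.61 instead of 0.80. These figures rest on assumed exercise shares, an assumed 1 to 3 added points, and an SD and effect borrowed from the primary outcome. They are an upper-end illustration. Pain-dependent exercising would understate a real benefit and would not create a false one. The primary outcome is a separate score obtained by telephone and is unaffected.

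### Investigator-recorded adverse events are filtered by presumed cause, and the unfiltered patient diary that could catch the rest ends at 72 hours

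*Combined protocol and SAP*

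**What the plan says.** The only adverse-event rule for investigators is one sentence in the outcome paragraph under Study Objectives: "Any adverse occurrences related to nerve blockade or prolonged bupivacaine effect will also be recorded". It does not say who decides that an event is related, on what criteria, or until when. No section provides for collecting events regardless of cause, or for grading severity or seriousness.

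Other safety information comes in by three routes, none with a relatedness filter:

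- **Diary.** Under Study Design and Methods, "the participants are to record oral opioid doses, use of other analgesics (such as acetaminophen), and any side effects that they encounter". The window comes from the same paragraph: "patients will record their NRS scores in a 72 hour postoperative diary".
- **Opioid side effects.** Nausea, vomiting and drowsiness are a secondary outcome (Study Objectives).
- **Chronic pain.** It is to be compared between groups (Study Objectives). The surgeon notes the patients who need referral (Study Design and Methods).

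On blinding, Study Design and Methods says that patients and the research team are blinded, that no effective placebo solution can be made, "so the surgeon will remain un-blinded", and that the surgeon stays out of data collection for the primary and secondary analyses. Statistical Considerations assigns Fisher's exact test to categorical variables. Opioid-related side effects are the only safety variable it names.

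**The concern.** A randomised saline group allows event rates to be compared without anyone judging cause. If cause is judged first and only the attributed events are written down, that advantage is lost for those events, and the unrecorded ones cannot be recovered at analysis.

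Two features of this trial make the filter more than a formality. Scientific Background describes the drug as effective elsewhere "but it hasn't been yet used for rotator cuff surgery", so choosing two causes in advance rests on little experience in this operation. Study Design and Methods also makes capsule closure a condition of injection because "liposomal bupivacaine is not approved for intra-articular use", and has every portal infiltrated. Yet neither the follow-up call nor the one-week visit has a stated question about joint or wound symptoms. At stake is how complete the trial's safety record is. No efficacy result or sample size depends on it.

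**Working it through.** The plan gives no adverse-event rate, capture rate or safety calculation, so there is no figure of its own to reproduce. The check sets the recording routes side by side and then gives a sense of scale.

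**1. Which events have a stated route?**

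| Event | Up to 72 hours | After 72 hours |
|---|---|---|
| Attributed to the block or to lasting bupivacaine action | Investigator rule; diary | Investigator rule, with no end date given |
| Nausea, vomiting, drowsiness | Secondary outcome; diary | None stated |
| Wound, joint or systemic event not so attributed | Diary, if the patient writes it down | None stated |
| Chronic pain | Not applicable | Noted by the un-blinded surgeon |

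The third row is the gap. The diary sentence lists side effects directly after opioid and analgesic doses, so a patient could read it as asking about medicines. Study Objectives describes the same diary as covering pain scores and opioid use only. The two sections also differ on who collects it: the surgeon (Study Objectives) or the research team (Study Design and Methods).

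**2. Is the criterion the same in both arms?** The block is plain bupivacaine or ropivacaine (Study Design and Methods).

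- Active arm, either block: bupivacaine received.
- Saline arm, bupivacaine block: bupivacaine received, from the block only.
- Saline arm, ropivacaine block: none received.

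Applied correctly, the second criterion cannot be met in the last group. The documents do not give the share of ropivacaine blocks. The first criterion, nerve blockade, applies to both arms alike.

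**3. What would unequal recording do?** Expected recorded events = 25 × true rate × proportion recorded. True rates are set equal in the two arms. All rates here are assumed.

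| True rate | Recorded, arm 1 / arm 2 | Expected recorded events | Spurious gap |
|---|---|---|---|
| 5% | 90% / 50% | 1.125 vs 0.625 | 2 points |
| 10% | 90% / 50% | 25 × 0.10 × 0.90 = 2.25 vs 25 × 0.10 × 0.50 = 1.25 | 4 points |
| 20% | 90% / 50% | 4.5 vs 2.5 | 8 points |
| 10% | 50% / 50% | 1.25 vs 1.25 | 0 points |

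Swapping the two proportions reverses the sign. Equal under-recording creates no gap but halves the counts.

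**4. What can 25 per arm show, even with full recording?**

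- Chance of at least one event in an arm, 1 − (1 − p)^25: 22% at p = 1%, 72% at 5%, 93% at 10%.
- One-sided 95% upper bound after 0 of 25: 1 − 0.05^(1/25) = 11.3%.
- Fisher's exact test, two-sided: 5 vs 0 gives p = 0.0502; 6 vs 0 gives p = 0.022.
- One event is 1/25 = 4 percentage points of an arm's rate.

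**The case against.** The strongest reply is that the sentence adds to other recording and does not replace it. Blinded patients in both arms write down any side effect for 72 hours. Opioid effects and chronic pain are collected separately, and the research team is blinded. A blinded person guessing at cause would lose events about equally in both arms, which creates no difference. No test of general adverse events is planned, so no stated safety comparison is distorted.

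Much of this stands, and it rules out several stronger readings that a reader might infer:

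- *Events enter the data only if attributed.* The diary contradicts this.
- *Wound or joint events would be recorded at 0% in both arms.* A patient can report early symptoms in the diary.
- *The un-blinded surgeon decides relatedness.* No section says so. The surgeon's exclusion is worded for the primary and secondary analyses, so it does not clearly cover adverse occurrences either, but that leaves the question open and does not show bias.
- *The plan names wound infection as an outcome risk.* The phrase "infection at the site of injection" is an eligibility exclusion. Intra-articular exposure is handled by design: an incompetent capsule is excluded, and a patient whose capsule cannot be closed is not injected.
- *The filter produces a large false difference.* This needs an extreme assumed split. With 20% true rates and 75% versus 25% recorded, 25 × 0.20 × 0.75 = 3.75 and 25 × 0.20 × 0.25 = 1.25 events are expected. Rounded to 4 vs 1, Fisher's p is about 0.35.

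The reply does not close the gap after 72 hours, the dependence on patients volunteering wound or joint problems, or the lack of an assessor, criteria and window in the investigator rule.

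**Conclusion.** The point holds in limited form. The plan makes presumed cause the entry criterion for investigator-recorded adverse occurrences and does not define how cause is judged. An event not attributed to the block or bupivacaine has only the 72-hour diary, and after that no stated route unless it is chronic pain. Such events can be missed in either arm.

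Differential recording is possible, because the bupivacaine criterion cannot truly apply to a saline patient with a ropivacaine block and because un-blinded attribution is not expressly excluded. It is not demonstrated. The gaps of 2 to 8 points shown above rest entirely on assumed true rates of 5% to 20% and assumed recording of 90% versus 50%; with equal recording the gap is zero.

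The amendment is worth making because it is cheap and improves what the trial can report on safety. It would not make 25 per arm adequate for comparing uncommon events.

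**What to change.** Replace the recording sentence under Study Objectives with wording such as: *All adverse events from study injection through the one-week visit will be recorded in both arms, whatever their presumed cause. Blinded research staff will ask about them at the day-after call and the one-week visit, including wound, joint and neurological symptoms. Relatedness will be recorded afterwards, by blinded staff, as a separate field.*

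Then:

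- Reconcile Study Objectives with Study Design and Methods on what the diary contains and who collects it.
- Add to Statistical Considerations that all-cause events are tabulated by arm with the Fisher's exact test already planned, labelled descriptive, and that relatedness is shown as a secondary listing.
- Keep the chronic-pain route for later follow-up. The one-week limit will still miss other late events, and the plan should say so.

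The cost is a wording amendment and a one-page form at two existing contacts for 50 patients. The downside is more unrelated minor events to list. Sample size and primary analysis are unchanged.

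### Chronic pain is to be compared between the groups, but no contact is scheduled after one week and cases enter only as referrals noted by the un-blinded surgeon at no fixed time

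*Combined protocol and SAP*

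**What the plan says.** The outcome paragraph under Study Objectives names the primary outcome, then the secondary outcomes, then adverse occurrences. It then adds that "the development of chronic pain at the surgical site will be assessed and compared between the two groups", with referral to the chronic pain service for patients in whom it occurs.

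Study Design and Methods gives the procedure. Patients report pain in the PACU and are telephoned about 24 hours after leaving the hospital. For the secondary analyses, "patients will record their NRS scores in a 72 hour postoperative diary". The last dated contact is the diary hand-over: "The pain diary will then be brought to the one-week follow up appointment". On chronic pain there is one sentence: "the surgeon will note any patient who develops chronic pain requiring referral to a pain management specialist".

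On blinding, the same section explains that no effective placebo can be prepared, "so the surgeon will remain un-blinded". It keeps the surgeon out of data collection for the primary and secondary analyses and adds: "By the time of the first surgical follow up examination, the outcomes will have been determined and recorded by investigators".

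Eligibility Criteria excludes "pre-existing chronic pain in the shoulder joint". Statistical Considerations does not mention chronic pain, either in the analysis or in the sample size.

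**The concern.** A promised comparison between randomised groups needs an outcome that is defined, looked for in everyone, and looked for at the same time. For chronic pain the plan provides none of these. The dated assessments stop at one week, before pain could reasonably be called chronic. After that, a case is recorded only if the surgeon notes it. A patient with persistent pain who is judged not to need referral, or who no longer attends, looks the same in the data as a patient who recovered.

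At stake is a sentence in the trial report. A statement that the groups did not differ in chronic pain, or that the drug reduced it, could be written from these data although they support neither.

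**Working it through.** The plan gives no figure for this outcome, so there is none to reproduce. The check sets the sections side by side.

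1. **Scheduled contacts (Study Design and Methods).** PACU; call at about 24 hours after leaving the hospital; diary to 72 hours; appointment at one week. Dated contacts after one week: 0. Dated assessments of chronic pain: 0.

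2. **Definition.** Neither Study Objectives nor Study Design and Methods gives a duration, an intensity threshold, an instrument or a time point.

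3. **Two descriptions of the outcome.** In Study Objectives the outcome is the development of chronic pain, and referral is its consequence. In Study Design and Methods what is noted is chronic pain that requires referral. The second set lies within the first, and the plan does not say which is to be compared.

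4. **What the comparison would estimate.** For group g, let p_g be the true proportion with chronic pain and d_g the probability that a case is noted. Ignoring false positives, the observed proportion is r_g = p_g × d_g, so r_1 / r_0 = (p_1 / p_0) × (d_1 / d_0).
   - If d_1 and d_0 differ, r_1 = r_0 is compatible with p_1 ≠ p_0, and r_1 ≠ r_0 is compatible with p_1 = p_0.
   - If d_1 = d_0 = d, then r_1 − r_0 = d × (p_1 − p_0), which is pulled towards zero by an unknown factor.
   - The plan supplies no information on d. Randomisation does not make d equal in the two groups, because noting happens after treatment and is done by someone who knows the allocation.

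5. **Blinding.** The safeguard that keeps the surgeon away from data collection is written for the primary and secondary analyses. Chronic pain is in neither list, and the surgeon is the only person assigned to record it.

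6. **What a fixed-time score would deliver.** Statistical Considerations plans 25 per group, so one call per patient is 2 × 25 = 50 calls. The approximate 95% half-width for a difference in mean NRS is 1.96 × SD × √(2/25) = 0.554 × SD. The documents state no SD. Over an assumed range:
   - SD 2.0: ±1.1 units
   - SD 2.5: ±1.4 units
   - SD 3.0: ±1.7 units

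   These assume that all 50 patients answer. The estimate would be imprecise but interpretable.

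**The case against.** The strongest reply is that this is an acute-analgesia trial. Its stated purpose concerns pain after the nerve block resolves; chronic pain is introduced as an addition, next to adverse occurrences and tied to onward care; and no hypothesis or sample size is attached to it. On that view it is a safety-type observation with one loosely worded verb. The status is correctly described, and it limits the importance of the point. It does not remove it, because the text promises a comparison and not merely a record.

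A second reply is that references to a first postoperative visit imply later ones, and that a single surgeon performs all the repairs. Later observation is indeed likely. But the plan neither schedules nor uses it, so its timing and completeness are undefined.

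Several stronger readings are tempting and should not be adopted:

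- **Follow-up ends at seven days, a small fraction of the time needed.** Any such fraction depends on a definition of chronic pain that the documents do not give, and it ignores the surgeon's open-ended noting after the first week.
- **All outcome collection is closed by the first follow-up.** The sentence saying so follows directly on the primary and secondary outcomes and is most naturally read as covering those.
- **Only completed referrals count.** The text speaks of pain that requires referral, which is not the same thing.
- **A null result is practically certain.** The documents give no event rate. Groups of 25 are small for any yes/no outcome, but that would hold equally with perfect ascertainment.
- **New pain cannot be told from old pain without a preoperative score.** Pre-existing chronic shoulder pain is an exclusion, and randomisation means that a comparison between groups does not need a baseline score to be unbiased.

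**Conclusion.** The point stands as a gap between a promised comparison and the means of making it. As written, the comparison would rest on passively noted referrals, recorded by an un-blinded observer over unspecified and possibly unequal follow-up. It could not support a conclusion in either direction.

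The extent is limited to one additional outcome. A reader might infer that the trial fails its objective; the documents do not support that, since the primary outcome and the listed secondary outcomes are collected by other means within the scheduled contacts. A reader might also infer that the surgeon's noting would favour one group. The plan leaves room for that but gives no evidence that it would happen or in which direction.

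The conclusion rests on reading the plan's silence as meaning that no later systematic enquiry is intended. If one is intended, it needs to be written down. The conclusion does not depend on any particular duration being used to define chronic pain. The change should be made, but it is not a reason to hold up the trial.

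**What to change.** Adopt one of two changes.

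(a) **Measure it in everyone.** The blinded research team, who already assess the patients, telephone every randomised patient at one prespecified time and ask for NRS pain at the operated shoulder. Three months is an example and an assumption; the sponsor should fix the time and justify it. Report the difference in mean score as an exploratory estimate with a 95% confidence interval, give the number reached in each group, and keep referrals as a safety listing. The outcome should then be named as pain at that time, because a single score does not by itself define a case of chronic pain. The cost is about 50 short calls and a later final data point for this outcome only. A preoperative NRS score is optional and would mainly add precision.

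(b) **Withdraw the comparison.** Delete the promise to compare the groups on chronic pain, report referrals as a descriptive count with each patient's length of follow-up, and state that the trial draws no conclusion on chronic pain. This needs a wording change and a record of the date each patient was last seen. The price is giving up a claim that the present plan cannot support.

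Neither option alters treatment, the sample size or the primary analysis.
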